1.8 Schedule of Visits, Questionnaires and Procedures

RESEARCH ACTIVITY	FORM NUMBER	PRESCREEN	SCREEN	BASELINE	WEEK 1	MONTH																		
						01	02	03	04	05	06	09	12	15	18	21	24	27	30	33	36			
Telephone Questionnaire	1	x																						
Assign Study ID			x																					
Informed Consent	2		x																					
Participant Information	3		x																					
Personal Information	4		x																					
Cardiovascular Disease History	5		x																					
Bleeding Assessment Questionnaire	6a, 6b		x		x	x	x	x	x	x	x	x	x	x	x	x	x	x	x	x	x	x	x	
Active/Passive Smoking Questionnaire	7a, 7b		x												x			x						x
Reproductive History (Female)	8		x																					
Medical History Baseline	9		x																					
Rose Questionnaire	10		x										x	x		x	x	x	x	x	x	x	x	
Claudication Questionnaire	11		x									x	x		x	x	x	x	x	x	x	x	x	
Cardiovascular Risk Factor Questionnaire	12		x																					
Non-study Medications	13,14		x	x		x	x	x	x	x	x	x	x	x	x	x	x	x	x	x	x	x	x	
Nutraceuticals and Supplements	15		x	x		x	x	x	x	x	x	x	x	x	x	x	x	x	x	x	x	x	x	
Blood Pressure	16		x	x		x	x	x	x	x	x	x	x	x	x	x	x	x	x	x	x	x	x	
Pulse Rate	16		x	x		x	x	x	x	x	x	x	x	x	x	x	x	x	x	x	x	x	x	
Weight	16		x	x		x	x	x	x	x	x	x	x	x	x	x	x	x	x	x	x	x	x	
Final Eligibility Checklist	17			x																				
Dietary Food Frequency	18			x					x			x		x		x		x		x		x		x
Soy Food Questionnaire	19			x				x			x		x		x		x		x		x		x	
7-Day Physical Activity Recall	20			x								x		x		x		x		x		x		x
CES-D*	21			x								x		x		x		x		x		x		x
Cognitive Assessment	22			x												x								x
Waist:Hip Circumference	23			x				x			x		x		x		x		x		x		x	
12-Lead Electrocardiogram	24			x										x				x					x	
Dispense Study Products	25			x		x	x	x	x	x	x	x	x	x	x	x	x	x	x	x	x	x		
Randomize Participant				x																				
Compliance	26					x	x	x	x	x	x	x	x	x	x	x	x	x	x	x	x	x	x	
Medication Termination/Dropout Form	27**																							
Adverse Events	28-38					x	x	x	x	x	x	x	x	x	x	x	x	x	x	x	x	x	x	
Medical History On-Trial	39													x				x			x		x	
Carotid Artery Intima-Media Thickness			x	x								x		x		x		x		x		x		x
Arterial Stiffness			x	x								x		x		x		x		x		x		x
Closeout Form	40																							x

*CES-D = Center for Epidemiologic Studies Depression Scale

**Use as needed

2.0

ORGANIZATIONAL STRUCTURE

3.1 Recruitment

Potential participants will be recruited from multiple sources, including the University of Southern California.

We plan to target recruitment of 50% women and 30% minorities for this trial (see Table below).

	American Indian or Alaskan Native	Asian or Pacific Islander	Black, not of Hispanic Origin	Hispanic	White, not of Hispanic Origin	Total
Female	1	6	11	18	84	120
Male	1	6	11	18	84	120
Total	2	12	22	36	168	240

3.2 Screening

Potential participants will be pre-screened with a Telephone Questionnaire **[FORM 1]** that will cover major inclusion and exclusion criteria. The study will be explained to potential participants at this time.

Individuals fulfilling the Telephone Questionnaire eligibility criteria and interested in the study will be scheduled for the screening visit (SV) and instructed to stop soy, soy protein and isoflavone food supplements one month prior to SV if currently taking any of these products.

Participants will be instructed to fast for 8 hours prior to SV.

Final study eligibility will be determined over SV and the baseline visit (v00).

1 week* 2 weeks
Telephone pre-screening ⇒ SV ⇒ v00 (randomization)

*1 month if potential participant needs to stop soy, soy protein and isoflavone food supplement intake prior to SV.

3.3 Screening Visit (SV)

A SV appointment is contingent upon fulfilling all pre-screening eligibility criteria **[FORM 1]**. At SV, the following will be performed:

1. Assign study identification (ID) number (see Section 3.4 for procedure)
2. Explanation of study aims, protocol, benefits, risks
3. Participants sign Informed Consent and HIPPA **[FORM 2]**
4. Participants complete forms covering contact and demographic information:
 - Participant Information Form **[FORM 3]**
 - Personal Information Form **[FORM 4]**

5. Pre-screening Telephone Questionnaire **[FORM 1]** eligibility criteria reviewed with participant
6. Ensure that soy, soy protein and isoflavone food supplements have been stopped at least one month prior to SV (see Section 3.2)
7. Administer the Cardiovascular Disease History Questionnaire **[FORM 5]** and confirm that participants have no clinical manifestations of cardiovascular disease.
8. Administer the baseline Bleeding Assessment Questionnaire **[FORM 6a]** and confirm that participants have no bleeding diatheses or bleeding tendencies
9. Participants administered baseline Smoking, Passive Smoking, Alcohol, Other Substance Use Questionnaire **[FORM 7a]**
10. Administer the Reproductive History Questionnaire **[FORM 8]** and confirm that female participants have not menstruated for at least 6 months
11. Participants administered questionnaires covering health information:
 - Medical History Questionnaire **[FORM 9]**
 - Modified Rose Questionnaire **[FORM 10]**
 - Claudication Questionnaire **[FORM 11]**
 - Cardiovascular Disease Risk Factor Assessment Form **[FORM 12]**
12. Administer the Nonstudy Medications Record **[FORMS 13,14]** and confirm that participants are not taking lipid-lowering medication
13. Administer History of Vitamin and Nutritional Supplement Use Questionnaire **[FORM 15]** and confirm that participants are not taking soy, soy protein and isoflavone food supplements
14. Obtain participant's blood pressure and pulse rate **[FORM 16]** and confirm that systolic blood pressure is ≤ 160 mmHg and diastolic blood pressure is ≤ 110 mmHg
15. Obtain and record participant's weight and height **[FORM 16]**
16. Carotid artery ultrasound examination performed (first baseline - see Section 4.2 for randomization procedure)
17. Fasting blood samples drawn and analyzed for:
 - Chemistry
 - CBC
 - Platelet count
 - Prothrombin (PT)/activated partial thromboplastin time (aPTT)
 - Lipids
 - C-reactive protein
 - Hemoglobin A1c
18. Fasting blood samples drawn and not analyzed until found eligible:
 - Insulin
 - Inflammatory markers
 - MCP-1
 - IL-8
 - TNF α
 - IL-1 β
 - IL-10
 - E-Selectin
 - P-Selectin

Baseline (randomization) visit (v00) is scheduled two weeks after SV to allow adequate sampling of baseline chemistry, CBC, platelet count, PT, aPTT, lipids/CRP and hemoglobin A1c. Participants will be instructed to fast for 8 hours prior to v00.

4.1 Visit 00 (v00)

1. Complete and review Final Eligibility Check List **[FORM 17]** and ensure that all eligibility criteria have been fulfilled before proceeding with randomization
2. Administer the Nonstudy Medications Record **[FORMS 13,14]** and confirm that participants are not taking lipid-lowering medication
3. Administer History of Vitamin and Nutritional Supplement Use Questionnaire **[FORM 15]** and confirm that participants are not taking soy, soy protein and isoflavone food supplements
4. Administer Dietary Food Frequency **[FORM 18]**
5. Administer Soy Food Questionnaire **[FORM 19]**
6. Administer 7-Day Physical Activity Recall Questionnaire **[FORM 20]**
7. Administer Center for Epidemiologic Studies Depression (CES-D) Scale **[FORM 21]**
8. Perform cognitive function assessment **[FORM 22]**
9. Obtain participants' blood pressure and pulse rate **[FORM 16]** and confirm that systolic blood pressure is ≤ 160 mmHg and diastolic blood pressure is ≤ 110 mmHg
10. Obtain and record participant's weight **[FORM 16]**
11. Measure and record waist:hip circumferences **[FORM 23]**
12. Obtain 12-lead ECG **[FORM 24]**
13. Carotid artery ultrasound examination performed (second baseline - see Section 4.2 for randomization procedure)
14. Perform urine dipstick
15. Fasting blood samples drawn and analyzed for:
 - Fibrinogen
 - vWF antigen
 - Tissue plasminogen activator (tPA)
 - Plasminogen activator inhibitor-1 (PAI-1)
 - D-dimers
 - Platelet aggregation (ADP, collagen, epinephrine)
 - Ristocetin cofactor
 - Factor VIII
 - Nattokinase
 - Anti-nattokinase antibodies
 - Erythrocyte sedimentation rate (ESR)
 - Red blood cell aggregation (plasma)
 - Red blood cell aggregability (polymer)
 - Plasma viscosity
 - Whole blood viscosity
 - Endothelial injury in-vitro assay: VCAM-1, ICAM-1
 - Monocyte activation (FACS): CD11b, CD11c, VLA-4
 - Storage
 - Plasma (EDTA) generic storage
 - Plasma (citrate) generic storage
 - Serum generic storage
 - Buffy coat
16. Active nattokinase/placebo nattokinase dispensed **[FORMS 25]**

17. Fill in the **study product ID number item** of the Eligibility Summary section on the Final Eligibility Check List **[FORM 17]** according to the randomization procedures in Section 4.2.

A follow-up clinic visit will be scheduled one week following v00. Subsequent clinic visits will be scheduled monthly (from date of randomization) for the first six months and then every three months for the remainder of the trial. Participants will be instructed to fast for 8 hours prior to each clinic visit.

4.2 Randomization Procedure

Active nattokinase and matching nattokinase placebo will be shipped directly to the DCC by Jarrow Formulas. Active nattokinase and matching nattokinase placebo will be shipped on different days separated in time by at least one week. Jarrow Formulas will clearly label the containers as active nattokinase and nattokinase placebo. Active nattokinase and matching nattokinase placebo capsules will be sealed in white plastic bottles with a quantity of 110 capsules per bottle. Each participant will be given adequate numbers of bottles of capsules for the period of time between clinic visits. The bottles of capsules will be prepared by the DCC for each randomized participant and will be dispensed at each clinic visit to each participant. The bottles of capsules will contain an attached label prepared with the following identifiers: Stratum (1,2) and a unique identification number for each bottle of capsules. The label will also contain space for the participant's name, visit number and date of dispensation to be filled in by clinic personnel when the bottle of capsules is assigned to a randomized participant.

The DCC will generate randomization lists for 2 strata with a blocking factor not identified to other study personnel:

- 1) Right distal common carotid arterial far wall IMT ≥ 0.75 mm
- 2) Right distal common carotid arterial far wall IMT < 0.75 mm

As the Final Eligibility Check List **[Form 17]** is completed and a participant is found to be eligible for randomization, the clinic coordinator will do the following:

- 1) Using the appropriate stratum (identified in the Eligibility Summary section of the Final Eligibility Check List **[Form 17]**, refer to the study randomization log for that stratum.
- 2) The study randomization log contains a separate list of sequential study product ID numbers for each stratum. Note that each stratum list has a column of study product ID numbers as well as a blank column to list the participant study ID. On the study randomization log for the appropriate stratum, write the participant study ID on the next available line. Note the study product ID number.
- 3) Write the study product ID number in the **product ID number item** of the Eligibility Summary section on the Final Eligibility Check List **[Form 17]**.
- 4) From the study product storage area containing study products that have not yet been assigned to randomized participants, obtain the bottle of capsules with the same study product ID number indicated on the randomization log and written on the Final Eligibility Check List **[Form 17]**.
- 5) For initial randomization, the bottle of capsules will contain enough capsules to last the participant for three study months (one bottle of capsules). Write the participant's name, visit number and date of dispensation on the label of the packet to be dispensed.

- 6) Duplicates of the study labels will be placed on the Nattokinase/Placebo Compliance Form **[Form 25]**.
- 7) Send the Final Eligibility Check List **[Form 17]** to the DCC.

Upon receipt of the Final Eligibility Check List **[FORM 17]**, the DCC personnel will do the following:

- 1) Review form for completeness and accuracy and enter the data.
- 2) Run error check routine to:
 - a) Confirm study eligibility.
 - b) Assure that the participant has been randomized within the appropriate stratum.
 - c) Inform the principal investigator and study coordinator if any of the above two protocol violations has occurred.
 - d) Generate an ideal visit schedule for the participant and send it to the ARU clinic. This ideal visit schedule will include ideal clinic visits every month for the first six months and then every three months for the remainder of the trial.
 - e) Generate labels for laboratory samples and distribute to clinic phlebotomist and core lipid laboratory personnel.

Only the right distal CCA far wall IMT at baseline will be used as a stratifying factor. Within each stratum, the distribution of other risk factors (specifically, LDL-C, smoking status, age and blood pressure) will be monitored across the two treatment groups. If imbalance is found across the two treatment groups, the randomization plan will be adapted to correct for this imbalance, i.e., adaptive randomization. These corrections will occur after the first 100 then 200 participants have been randomized.

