1.3 Study Overview

The Nattokinase Atherothrombotic Prevention Study (NAPS) is a randomized, double-blinded, placebo-controlled, non-invasive vascular imaging trial. A total of 240 healthy non-demented women and men without clinical evidence of CVD or diabetes mellitus will be randomized to either placebo or to active oral nattokinase 2,000 fibrinolytic units daily. Recruitment will occur over 2 years and the treatment period will be for 3 years. Candidates will be prescreened, seen for 1 screening visit to determine eligibility and then randomized at a baseline visit. Participants will then return for a follow-up visit 1 week after randomization and then will be followed monthly for the first 6 months and then every 3 months for the remainder of the trial. Rate of change in distal common carotid artery (CCA) far wall intima-media thickness (CIMT) and arterial stiffness in computer image processed B-mode ultrasonograms will be the co-primary trial end points. Cognitive decline determined with a neuropsychological battery designed to evaluate 7 cognitive domains including: attention, concentration, working memory, executive function; visuospatial/visuoconstructive skills; naming/semantic memory; and verbal and nonverbal episodic memory will be the secondary trial endpoint. Other endpoints will include blood pressure, hemostatic, fibrinolytic and hemorheological factors as well as platelet activity and biomarkers for inflammation, monocyte activation, vascular endothelium injury and activation of vascular endothelium by circulating monocytes.

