9.6.5.1 Primary Efficacy Analysis: Carotid Artery IMT Analyses

The primary end point will be the per-subject rate of change in the right distal CCA far wall IMT. The rate of change in the right distal CCA far wall CIMT will be computed for each participant by fitting a regression line of CIMT on years since baseline ultrasound. The estimated slope of the regression line will be used as that subject's CIMT rate of change. Analyses of trial end points will be performed on the intent-to-treat sample, which will be defined as all randomized participants who had a baseline and at least 1 follow-up CIMT measurement taken after randomization.

The statistical approach outlined above will be accomplished using mixed effects models for longitudinal data, with the randomization stratification variable (dichotomized baseline CIMT) used as a covariate. Each CIMT measure will be included as a dependent variable. The regression coefficient associated with the model covariate of time on-study will estimate the average group progression rate of CIMT (in mm/year). Random effects terms for the regression intercept and slope (change over time) will allow for individual participant deviations from their group average in baseline CIMT and CIMT rate of change, respectively. The statistical test for differences in the CIMT rate by treatment group will be accomplished by adding a treatment group by time on-study interaction term. The significance of the regression coefficient associated with this interaction term is the test that the CIMT rates differ by treatment group. We will also evaluate baseline plasma levels of insulin, lipids/CRP, hemoglobin A1c, coagulation factors, rheology parameters and inflammatory variables, dietary nutrients, smoking, blood pressure, physical activity and use of non-study medications as potential confounders. If any of these variables are found to be confounders of treatment-rate of CIMT relationship, they will be included as

covariates in the analysis.

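### LDL-C, smoking, age and blood pressure may steer up to 140 of 240 allocations, but no outcome model pre-specifies them

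*Combined protocol and SAP*

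**What the plan says.** Section 1.3 sets the size: "A total of 240 healthy non-demented women and men without clinical evidence of CVD or diabetes mellitus will be randomized". Section 4.2 describes the base scheme: "The DCC will generate randomization lists for 2 strata with a blocking factor not identified to other study personnel". The clinic coordinator takes the next line of a log: "The study randomization log contains a separate list of sequential study product ID numbers for each stratum".

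Section 4.2 then states "Only the right distal CCA far wall IMT at baseline will be used as a stratifying factor", but adds "Within each stratum, the distribution of other risk factors (specifically, LDL-C, smoking status, age and blood pressure) will be monitored across the two treatment groups". The consequence is conditional: "If imbalance is found across the two treatment groups, the randomization plan will be adapted to correct for this imbalance, i.e., adaptive randomization". On timing: "These corrections will occur after the first 100 then 200 participants have been randomized". No imbalance measure, threshold, algorithm or allocation probability is given, and the text does not say how a next-line log would carry out covariate-dependent allocation.

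On the analysis side, 9.6.5.1 fits a mixed model "with the randomization stratification variable (dichotomized baseline CIMT) used as a covariate" and tests the interaction of treatment with time on study. Baseline lipids, smoking and blood pressure belong to a longer list of possible confounders, added only if found to be such, with no stated criterion. Age is not on that list; among the outcome analyses it is named only as a possible effect modifier (9.6.7.2). Section 9.6.5.2 carries the same approach over to stiffness. Section 9.6.5.3 (cognition) fixes the CIMT stratum and the baseline cognitive score, and has no confounder step.

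**The concern.** Variables that help determine allocation normally belong in the outcome model. The plan follows this for the CIMT stratum but not for the four factors that may steer later allocations.

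Forcing balance on a prognostic factor reduces the true sampling variance of the treatment contrast. A model that omits the factor still counts its contribution as residual noise, so the reported standard error is too large and the test rejects less often than its nominal level. The precision available from measurements already taken is given up as well.

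The confounder step is a weak safeguard. Once allocation has balanced a factor, adding it hardly moves the treatment estimate, so a rule based on change in the estimate tends to leave it out. Age cannot enter by that route at all.

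**Working it through.** **Inputs from the plan.** N = 240; two CIMT strata with blocked lists; four monitored factors; corrections after 100 and 200; only the CIMT stratum fixed in the CIMT and stiffness models. The text gives no slope SD, effect size or power figure to reproduce, and this is not counted as a fault. Two-sided 0.05 is stated in 9.6.2 and 9.6.3 and is assumed here for the primary test.

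**Allocations exposed.** After the first check: 240 − 100 = 140, and 140/240 = 58.3%. If only the second check triggers: 240 − 200 = 40, and 40/240 = 16.7%.

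**Analytic limit.** If balance were perfect and the factors explained a share R² of the variance in slope, the stratum-only model would overstate the standard error by 1/√(1 − R²). The true two-sided level would be 2[1 − Φ(1.960/√(1 − R²))]:
- R² = 0.05: SE ratio 1.026; level 0.044
- R² = 0.10: SE ratio 1.054; level 0.039
- R² = 0.20: 1.960/√0.80 = 2.191; level 0.028

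**Simulation of the plan.** 8,000 trials per scheme. Assumptions: 1:1 allocation, blocks of 4, 10% smokers, the four factors contributing equally to R², complete data. At 100 and 200 each factor was checked within each stratum; a flagged stratum moved to a covariate-balancing biased coin. The outcome was the per-subject slope, so a covariate here corresponds to a covariate-by-time term in the mixed model. Monte Carlo SE is √(0.05 × 0.95/8,000) = 0.0024.

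Type I error:

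| R² (assumed) | Stratum only, fixed blocks | Stratum only, trigger p<0.05, coin 0.8 | Stratum only, trigger p<0.20, coin 0.8 | Stratum only, always adapt, coin 0.9 | All four factors added, three adaptive schemes |
|---|---|---|---|---|---|
| 0 | 0.048 | 0.049 | 0.051 | 0.049 | 0.048–0.051 |
| 0.05 | 0.050 | 0.050 | 0.044 | 0.041 | 0.047–0.052 |
| 0.10 | 0.053 | 0.047 | 0.041 | 0.041 | 0.047–0.049 |
| 0.20 | 0.048 | 0.046 | 0.039 | 0.028 | 0.048–0.050 |
| 0.30 | 0.055 | 0.046 | 0.034 | 0.024 | 0.050–0.051 |

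The always-adapt column agrees with the analytic limit within Monte Carlo error for R² up to 0.20.

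**How often a check would trigger.** At participant 100 at least one flag arose in 33% of trials (p<0.05) or 85% (p<0.20). As a rough check, eight independent comparisons (four factors, two strata) give 1 − 0.95⁸ = 34% and 1 − 0.80⁸ = 83%.

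**Does the confounder step repair it?** The plan gives no rule, so a 10% change-in-estimate rule was tried, with age not eligible. Type I error under the adaptive schemes was 0.025–0.051, and under always-adapt it was essentially that of the stratum-only model.

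**Power.** The reference effect is (1.960 + 0.842) × √(4/240) = 0.362 SD, which gives 80% at N = 240. Across the four schemes:
- R² = 0.10: stratum only 0.80–0.81; with all four factors 0.83–0.84
- R² = 0.20: stratum only 0.80–0.83; with all four factors 0.87–0.88

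**The case against.** Several points on the other side stand.

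- Adaptation is conditional. With a p<0.05 trigger the stratum-only level was 0.046–0.050, which is immaterial.
- The error is in the safe direction. A reader might infer that unmodelled adaptive allocation raises the false-positive rate; neither the formula nor the simulation shows that.
- A reader might infer that adaptation costs power against the planned level. It does not: stratum-only power stayed at about 0.80 or slightly above. What is forgone is the gain from adjustment, and that is forgone under fixed blocks too.
- A reader might infer that late allocations become predictable at the clinic, since staff there record or see these factors. That requires someone to learn the direction of the correction. The documents show no such route: the data coordinating center generates the lists and the coordinator sees product numbers.
- A reader might calculate that erasing a 0.2 SD gap at 100 per arm forces the last 20 per arm to differ by 100 × 0.2/20 = 1.0 SD. This ignores the correction already made at 100 and the monitoring within strata, and assumes complete cancellation, which the plan does not require.

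The confounder step can admit three of the four factors, so the plan is not silent on them. It gives no selection rule and excludes age, so this answers the point only in part.

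**Conclusion.** The mismatch is real and the remedy is cheap, but it does not threaten validity. If allocation is adapted and the four factors predict the outcome, the stratum-only CIMT and stiffness tests are conservative: about 0.04 at R² = 0.10 and 0.03 at R² = 0.20 under strong adaptation, and close to 0.05 if adaptation is rare or R² is small. Adding all four factors brought the level to 0.047–0.052 in every adaptive scheme tried and gave a modest gain in power when R² was 0.10 or more.

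These sizes rest on assumed values of R², trigger, coin probability and block size, none of which the plan states. Cognition was not simulated; the same reasoning applies because its model holds none of the four factors. The results do not show that the adaptation itself must be removed: with the factors in the model, covariate-adaptive allocation performed properly.

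**What to change.** - **9.6.5.1 and 9.6.5.2:** always include baseline LDL-C, smoking status, age and blood pressure alongside the CIMT stratum, whatever their observed imbalance. Each needs its interaction with time on study, because the test compares slopes and a main effect alone would adjust only the level. For these four this replaces the data-driven confounder selection. State which blood pressure measure is used and how smoking is coded, and use pre-randomization values.
- **9.6.5.3:** add the same four baseline covariates. The outcome is already change from baseline, so main effects suffice for the overall treatment comparison.
- **4.2:** if the adaptation is kept, state the imbalance measure, threshold and algorithm, and how the sequential lists are replaced. Keeping the two blocked lists for all 240 and using the monitoring as a report only is an acceptable alternative, not a requirement.

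The cost is wording. All four factors are already collected. With one term per factor, the slope models use about eight degrees of freedom (four main effects and four time interactions), which is small for 240 participants. If the factors turn out not to predict the outcome, almost nothing is lost: at R² = 0, adjusted power was 0.79–0.80 against 0.79–0.80 unadjusted.
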